Primary care patients will be recruited and assessed pre and post intervention and at 16 and 24 week follow-up time points. Each quarter, two months will be spent recruiting and 1 month will be used to conduct the intervention groups. Ideal group size is 6 participants. We anticipate running up three consecutive groups (PCBMT and EDU) at each of the two sites. However, our timeline allows for addition groups as needed. To be eligible, participants must be 1) enrolled in primary care at the Syracuse or Canandaigua VAMC and 2) report significant PTSD symptoms (qualifying criterion A traumatic event plus at least a 31 on the PCL-5). Exclusion criteria are minimized because we seek to include any primary care patients with troubling PTSD symptoms that would normally receive treatment in primary care. Patients will be excluded if they demonstrate symptoms that would not allow them to actively participate in PCBMT: 1) gross cognitive impairment ( $>16$  on the Blessed OMC), 2) suicide attempt or desire to commit suicide in the last month (as measured by P4 screener). To allow the study to isolate the effects of the intervention and ensure patient treatment preferences are honored, patients will be excluded if they 3) have received psychotherapy or change in psychiatric medication outside of VHA primary in the last 2 months, or 4) voice a preference to be directly referred to specialty mental health care. Veterans with depression, anxiety disorders, mild TBI, and alcohol/ substance use disorders will not be excluded, because these problems commonly co-occur with PTSD, and individuals with these conditions have previously benefited from mindfulness training. Patients who receive PC-MHI services will not be excluded, as this is part of the usual primary care services that all Veterans can receive.

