**C.2.3 Phase 2 Procedures:** The baseline session will include informed consent process (Appendix 2) followed by administration of study measures. Participants will be screened for cognitive impairment with the Blessed Orientation Memory and Concentration measure and suicidality with P4 Screener. The P4 Screener assessed past history, plan, probability, and preventive factors and then classifies respondents as minimal, lower or higher risk for suicide. At the baseline assessment, higher risk participants will be connected to VHA Suicide Prevention Services prior to continuing them in the study. In addition to assessing primary outcomes and patient safety, we plan to test the feasibility of measuring concerns that commonly co-occur with PTSD (depression, insomnia, pain, and alcohol/substance misuse) and potential mediators of the relationship between receiving mindfulness training and changes in PTSD symptoms and psychosocial functioning (mindfulness and emotion regulation skills). Pilot data in this area will help us plan for a future full-scale investigation of potential mediators. Post-treatment assessment will occur upon completion of the assigned intervention. We will re-assess participants at two follow-up points: 16 weeks and 24 weeks post-baseline. This will allow the opportunity to test the feasibility of retaining participants over time so that in the full-scale future trial we can test if any changes observed post-treatment are maintained over time. Given that an aim of this line of research is for PCBMT to serve as a bridge to other more intensive PTSD treatments, within the full-scaled trial, data from the 24 week follow-up will also allow the ability to measure changes associated with any new treatments initiated post study treatment. All research assessments will be administered by research staff blinded to randomization outcome. Participants will be reimbursed \$25 per assessment (\$100 total). Randomization will be stratified based on baseline PCL-5 scores (31-40 vs.  $>40$ ) to equate groups at baseline.

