##### Aim 2.a. (recruitment and study retention)

- Number of participants screened per month
- Number enrolled per month
- Proportion of screened participants who are eligible to enroll
- Completion rates of follow-up assessments

Aim 2.b. (participant adherence and retention in treatments, provider and peer treatment fidelity)

- Retention rates in both study interventions
- PCBMT facilitator fidelity. PCBMT facilitators will complete a checklist of essential elements after each class. Co-I's [name] or [name] will observe 25% of all classes and independently rate the fidelity assessment piloted in our earlier PCBMT study (Appendix 3). This assessment was developed based on the guidelines published by Borrelli et al. and documents observations on the delivery and enactment of treatment skills.

Aim 2.c. (intervention acceptability) will be measured at post-treatment by 2 measures.

- The *Client Satisfaction Questionnaire (CSQ)* is an 8-item self-report measure with strong psychometric properties: higher scores are related to treatment completion and symptom reduction.
- *Intervention Acceptability* is a self-report measure created for this study to assess participants' reactions to their assigned intervention, including perceived helpfulness of core intervention components, specific symptoms or functional concerns that improved, and if and how the intervention contributed to meeting the participants' personal recovery goals. Retention (# of sessions attended) will also contribute to measuring intervention acceptability.

Aim 2.d.i. (patient functional status) will be measured at baseline, post-treatment and 16 and 24 week follow-up by 3 measures.

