**C.2.5. Intervention Conditions:** The PCBMT and EDU groups will share several structural features: both will be 1) located in primary, 2) co-led by a licensed mental provider (psychologist, clinical social worker, mental health counselor) and a Veteran peer support specialist, 3) consist of four 90-minute weekly sessions, 4) Peers will meet briefly (30 minutes) to guide participants in completing the Personal Health Inventory (PHI) prior to starting their assigned treatment condition. The PHI was developed by the VHA Office of Patient Centered Care and Cultural Transformation and is a commonly used by VHA peers support specialists. The PHI will allow participants to engage in self-reflection regarding what matters most to them in their lives (Appendix 4). This discovery process will inform the identification of personal health goals that align with their values and priorities, and thus ideally increase patient activation and engagement. This process supports the delivery of personalized, proactive, and patient-driven care. Completed PHIs will be shared with the group facilitators to help personalize the intervention. 4) During the meeting with the peers, participants will also watch a video to orient them to their assigned condition. PCBMT participants will watch the 7-minute "What is Mindfulness?" video from the VHA OPCC. EDU participants will watch two 3.5-minute whiteboard videos "What is PTSD?" and "Treatment: Know Your Options" from the VHA National Center for PTSD. 6) Printed instructions for homework will be provided and participants will be asked to submit simple forms during each class that record the type and number of minutes of at home practice completed. For PCBMT this will include time spent in

formal and informal meditation. 7) Peer co-leaders will act as peer-navigators to help participants connect to any additional MH, case management, or medical care needed.

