### C.3 Analysis Plan

Aim 1: Gather VHA mental health treatment provider and peer feedback to adapt PCBMT. Co-I [name] will oversee Aim 1 analyses using a Rapid Assessment Process (RAP). This approach is ideal when data needs to be collected and analyzed in one year or less, when only key informants will be interviewed, and when analyses will be deductive. The PI and project coordinator will conduct interviews together with the PI primarily asking questions and the coordinator typing detailed field notes to document responses. A template will be created with a domain name for each interview question (e.g., activating patients, peer roles). The PI, coordinator, and [name] will review the first few sets of field notes collaboratively and summarize content into the domains on the template. After consistency is reached, coders will review the remaining field notes ( $\approx 7$ ) independently. Led by [name], coders will then meet again to analyze summaries and identify suggestions for revisions or aspects seen as helpful that should be maintained within each domain. The PI and Co-Is [name], [name] and [name] will then meet and collectively decide how to modify the protocol. Modifications will only be made if the resulting PCBMT protocol is: 1) feasible to deliver in VHA primary care and 2) stays true to the core mindfulness components. Modifications will be prioritized that are expected to 3) help Veterans develop skills for PTSD symptom management, 4) increase the training’s patient-centeredness, and 5) will affect multiple qualitative domains.

Aim 2: Conduct a pilot RCT (N=60 randomized, n=48 completers) comparing PCBMT to EDU.

**2a.** As this trial will provide us with feasibility information for a larger trial, we will describe the number of participants screened and enrolled per month, proportion of screened participants who are eligible to enroll, completion rates of follow-up assessments, retention rates in study conditions, and the rate and timing of patient drop-out. Recruitment over twelve months will be displayed by plotting the cumulative number of patients enrolled into our study and compared to the anticipated rate of recruitment. Graphs will also be utilized to display rates of intervention and assessment retention at each measurement time. Ninety five percent confidence intervals will be calculated and used in design considerations of a larger trial.

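### Does timing the post-treatment visit by completion of the intervention leave out participants who never start or who stop early?

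*Combined protocol and SAP*

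**What the plan says.** Section C.2.3 (Phase 2 Procedures) ties the visit to an event: "Post-treatment assessment will occur upon completion of the assigned intervention". The two later visits are fixed at 16 and 24 weeks from baseline. Section C.2.1 gives the overall schedule: "Primary care patients will be recruited and assessed pre and post intervention and at 16 and 24 week follow-up time points". Under C.2.5 both arms "consist of four 90-minute weekly sessions", and C.2.1 sets aside one month of each quarter for running the groups, after two months of recruiting.

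In C.2.4, acceptability (Aim 2.c) "will be measured at post-treatment by 2 measures", namely the CSQ and a study-specific acceptability form. Neither is scheduled at any other time. The same section adds that "Retention (# of sessions attended) will also contribute to measuring intervention acceptability".

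The Aim 2 analysis in C.3 opens with "Conduct a pilot RCT (N=60 randomized, n=48 completers) comparing PCBMT to EDU". It promises graphs of "rates of intervention and assessment retention at each measurement time", and it reports separately how many participants drop out and when. Multiple imputation is planned for missing data.

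**The concern.** *Completion* has two possible meanings: the end of the group's course, or the individual's own finishing of it. On the second meaning, a participant who attends no class never reaches the event that triggers the visit, and the plan gives no substitute date.

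Three consequences would follow from that meaning. First, the CSQ and acceptability results would describe mainly people who finished. C.2.4 itself says of the CSQ that "higher scores are related to treatment completion and symptom reduction", so the likely direction of error is upward. Second, the post-treatment retention rate would depend on who is counted as due. Third, if completion meant all four classes, everyone with a CSQ score would have attended four. Imputation could then not learn how satisfaction varies with attendance.

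Study retention and acceptability are pilot aims (2.a and 2.c) meant to inform a larger trial. Non-attendance is also a known risk: the introduction reports that 55% of Veterans came to the first class of the earlier version. An unasked questionnaire cannot be recovered later.

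**Working it through.** **The plan's own figures.** Sections C.2.1 and C.2.2 give 5 participants per month for one year: 5 × 12 = 60, as stated. C.3 gives 48 completers: 48/60 = 80%. The plan does not say whether a completer is someone who finished treatment or someone who finished assessment.

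**Which meaning of completion fits the other sections?**

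1. *The course has a calendar end.* Four weekly sessions fit the one month per quarter that C.2.1 reserves for groups. The date of a group's last class is therefore known whoever attends.
2. *No completer restriction appears.* C.2.1 says patients are assessed before and after the intervention. C.2.4 lists the functional outcomes at baseline, post-treatment, 16 and 24 weeks. Neither limits post-treatment to finishers. C.2.3 budgets four payments per participant: 4 × $25 = $100. This is weak evidence, since payment is made per assessment.
3. *Two retention measures are kept apart.* C.2.4 puts completion of assessments under Aim 2.a and retention in the interventions under Aim 2.b. C.3 plots both at each measurement time. If only treatment completers were due at post-treatment, treatment completion would largely fix the assessment rate there, and the second curve would add little.
4. *An event anchor has a practical reason.* Participants wait for a group to form. With a wait of 0 to about 9 weeks (two recruiting months) plus 4 weeks of classes, the course ends roughly 4 to 13 weeks after baseline. A fixed week would catch some people before their group had finished. The end of the group's course suits everyone and still falls before week 16.

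All four points agree with the group-end meaning, and the third argues directly against the individual meaning.

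**What each meaning implies for retention.** Suppose, for illustration, that the 48 are treatment completers and that they alone are assessed. The Wilson 95% interval is (p + z²/2n ± z√(p(1−p)/n + z²/4n²)) / (1 + z²/n), with z = 1.96.

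| Denominator | Rate | 95% CI |
|---|---|---|
| 60 randomized | 48/60 = 80% | 68.2% to 88.2% |
| 48 counted as due | 48/48 = 100% | 92.6% to 100% |

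The second row requires dropping all 12 non-completers from those due. C.3 gives no basis for that, and its drop-out report would make the 12 visible. On the group-end meaning all 60 are due, and only the first row remains.

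**What the individual meaning could do to the CSQ.** The error in a completer-only arm mean is the non-completion share times the gap between completers and non-completers. The share is 20% (12/60). The documents give no gap; assume 0.5 to 1.0 SD.

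- Error: 0.20 × 0.5 = 0.10 SD, up to 0.20 × 1.0 = 0.20 SD.
- Half-width of the 95% interval with 24 of 30 responding (equal allocation assumed): t(0.975, 23)/√24 = 0.422 SD.
- Ratio: 0.10/0.422 = 24%, up to 0.20/0.422 = 47%.

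Even on these assumptions the error is under half of the interval's half-width. It also presumes that the target is the mean over everyone randomized, which C.3 does not say, and that no imputation is done, although imputation is planned.

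**The case for a change.** The strongest reply is that the plan should not depend on a sensible reading. It uses calendar anchors for the 16- and 24-week visits and drops them at the one visit where the CSQ is taken. Two sites could apply the sentence differently. A missed PCL-5 at post-treatment is partly informed by later scores, whereas a missed CSQ has no later measurement. Imputation sets neither a visit date nor a denominator. Attendance counts show that people left but not what they found unhelpful.

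Much of this is accurate. No section dates the visit for a non-starter, and no section names the retention denominator. Even on the group-end meaning, someone who withdraws before a group is scheduled has no date; that person would simply count among the 60 as not assessed.

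The step from silence to harm does not stand. It needs staff to withhold a planned and paid assessment from participants still in the study, on a meaning that the rest of the plan speaks against. The 55% figure comes from a version with an outside facilitator and no peers, and peer support was added partly to raise participation. It is a worst case rather than a forecast. Non-starters can also say little about class components they never received, so a written rule would bring in limited acceptability data from them.

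**Conclusion.** The concern identifies missing detail that a trial team would fill in the obvious way: assess everyone when the assigned group's course ends, and divide by the number randomized. Read so, the retention rate has one value for any given count (80% if 48 of 60 are seen), and the CSQ is offered to people whatever their attendance. The 80%-or-100% contrast and the 0.10 to 0.20 SD error arise only if treatment completers alone are assessed. They also rest on an undefined completer count and, for the CSQ, on a gap that the documents do not supply.

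The setting limits the stakes further. The pilot is sized on recruitment rate, acceptability is summarized descriptively, and the plan sets no progression threshold on either measure. Sessions attended counts toward acceptability without depending on the visit, and the extent and timing of drop-out are reported. Giving the number who answered the CSQ, alongside attendance, is ordinary reporting practice. No change to the plan is needed.

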- *PTSD Checklist-5 (PCL-5)* is a 20-item self-report measure that asks respondents to rate how much they have been bothered by DSM-5 PTSD symptoms in the past month. We will administer this with the extended assessment of traumatic events to ensure that the symptoms reported are related to an event that meets criteria for a traumatic event. Early psychometric study of the PCL-5 indicates excellent reliability and validity. A cut point of 31 along plus meeting Criterion A will be required for study inclusion to allow Veterans with subthreshold PTSD to participate. The total score will be used to indicate PTSD severity at each time point. Since participants must wait to begin the intervention until enough participants are enrolled to form a group, the PCL-5 will be re-administered if participants do not attend class 1 within one month of their baseline interview.
- *Recovery Assessment Scale (RAS)* is a 24-item self-report measure that will assesses various aspects of recovery from the perspective of the Veteran, with an emphasis on hope and self-determination. It covers 5 domains: personal confidence and hope; willingness to ask for help; goal and success orientation; reliance on others; and no domination by symptoms. It has high reliability and good concurrent validity.
- *Patient Health Questionnaire-9 (PHQ-9)* assesses 9 symptoms of depression on a 4-point scale. Participants who endorse the suicidality item will also be administered the P4 screener which assess past history, plan, probability, and preventive factors for suicide.
- *Health Promoting Lifestyle Profile II*

Hypothesized mediators will be assessed with 2 psychometrically sound measures at each time point.

- *Self-Compassion Scale- Short Form*
- *Five Facet Mindfulness Questionnaire (FFMQ)* is a 39-item scale measuring observing, describing, acting with awareness, non-judging, and non-reactivity.
- *Emotion Regulation Questionnaire (ERQ)* is a 10-item self-report measure designed to assess the use cognitive reappraisal and expressive suppression.

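### Does timing the 16- and 24-week follow-ups from baseline, while patients wait for a group to form, spoil the follow-up results?

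*Combined protocol and SAP*

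**What the plan says.** The protocol runs two clocks. In C.2.3 the first assessment after baseline follows treatment: "Post-treatment assessment will occur upon completion of the assigned intervention". The two later ones follow enrolment: "We will re-assess participants at two follow-up points: 16 weeks and 24 weeks post-baseline".

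The gap between the clocks varies because treatment is given in groups. C.2.4, under the PCL-5, explains the delay: "Since participants must wait to begin the intervention until enough participants are enrolled to form a group". It also provides for long delays: "the PCL-5 will be re-administered if participants do not attend class 1 within one month of their baseline interview". That month triggers a repeat questionnaire; it is not a limit on the wait. C.2.1 gives the cycle: "Each quarter, two months will be spent recruiting and 1 month will be used to conduct the intervention groups". C.2.5 has both arms "consist of four 90-minute weekly sessions".

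C.3, under 2.d.i, plans means, plots and effect sizes at each visit and a multi-level model for group by time. It does not say whether time enters as visit number or as weeks, and the wait is not among the quantities to be reported.

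**The concern.** Two patients seen at the same nominal 16-week visit may be at quite different distances from their last class. C.3 intends the effect sizes and plots to inform a larger trial, and C.2.3 says that "in the full-scale future trial we can test if any changes observed post-treatment are maintained over time". A designer who reads the pilot's 16-week effect as the effect a fixed time after treatment would be misled about how quickly benefit fades, or whether it fades at all.

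The open time variable adds to this. If time were entered as nominal weeks, as though everyone began class at baseline, the estimated weekly change after treatment would be too small. The repeat PCL-5 does not settle the matter. It refreshes one measure before treatment and leaves the time since treatment as it was.

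**Working it through.** The documents give no figure for time since treatment, so there is none to reproduce.

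**Inputs**
- Follow-ups at 16 and 24 weeks from baseline (C.2.3).
- Four weekly sessions, hence 3 weeks from first to last class (C.2.5).
- Wait *w* from baseline to class 1. No maximum is stated, so two scenarios are assumed: up to one month (the repeat-PCL-5 trigger, C.2.4) and up to two months (the recruiting window, C.2.1), with enrolment uniform over the period and a minimum wait of zero.
- One month = 365.25/12/7 = 4.35 weeks.

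**Time since the last class**
- 16-week visit: 16 − 3 − *w* = 13 − *w*.
- 24-week visit: 24 − 3 − *w* = 21 − *w*.

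| Longest wait | Mean wait | 16-week visit: range (mean) | 24-week visit: range (mean) |
|---|---|---|---|
| None | 0 | 13.0 | 21.0 |
| One month | 2.17 | 8.7–13.0 (10.8) | 16.7–21.0 (18.8) |
| Two months | 4.35 | 4.3–13.0 (8.7) | 12.3–21.0 (16.7) |

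Counting treatment as four weeks lowers every time since the last class by one week. The spread stays the same, because it is the spread of the waits.

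**Effect on the visit-specific effect size**

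Suppose the between-arm effect falls linearly by *L* over the 13 weeks after treatment (an assumption, not a figure in the documents). The mean effect at the 16-week visit then differs from its no-wait value by (*L*/13) × mean wait.

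| *L* (SD) | One month | Two months |
|---|---|---|
| 0.10 | 0.02 | 0.03 |
| 0.25 | 0.04 | 0.08 |
| 0.50 | 0.08 | 0.17 |

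For precision, C.3 gives "Conduct a pilot RCT (N=60 randomized, n=48 completers) comparing PCBMT to EDU". Taking 24 completers per arm, the 95% half-width of an effect size near zero is 1.96 × √(2/24) = 0.57 SD. The largest shift in the table is under a third of that (0.17/0.57 = 0.30).

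**Effect on the model's slope**

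This depends on how time is coded.
- *Nominal weeks, wait ignored.* Post-treatment times are taken as 0, 13 and 21. Centred, they are −11.33, 1.67 and 9.67, with sum of squares 224.67. The slope is understated by 11.33 × mean wait / 224.67, which is 11.33 × 2.17/224.67 = 11% (one month) or 11.33 × 4.35/224.67 = 22% (two months).
- *Actual weeks from baseline.* The three times are 3 + *w*, 16 and 24. Within a person the gaps between visits are now correct. With equal correlations of 0.6 and uniform waits, the understatement is 0.2% (one month) or 0.8% (two months).
- *Visit as a category.* No weekly slope is fitted, so the question does not arise.

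The 11% and 22% therefore come from one particular coding, which the plan does not state. Timing the visits from baseline does not by itself produce them.

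**The case for a change.** The strongest case for acting is that the remedy is cheap and the information useful. It would take one class-1 date per cohort, a short table of waits by arm, and a second model fit on a clock that starts at class 1. The width of the pilot's intervals does not tell a designer what time point was measured. The wait is also a feasibility quantity in its own right for a group-based trial, yet it is absent from the metrics in C.2.4 and C.3.

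Part of this stands. C.3 is silent on both the wait and the time variable, and a sentence on each in the report would help the reader. The dates should largely be to hand: the one-month rule already obliges staff to compare class-1 attendance with the baseline interview.

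The second model is harder to defend. At any one visit, weeks since class 1 is 16 (or 24) minus the wait, so the fit cannot fully separate time since treatment from an effect of waiting. On that clock the baseline visit falls at minus *w*, and a single linear term would mix the waiting period with change after treatment. It would also be imprecise. A 0.25 SD loss over 13 weeks is a slope of 0.25/13 = 0.019 SD per week, against a simulated standard error of about 0.015 (24 per arm, correlation 0.6), a ratio of about 1.3.

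One limit cuts the other way. Two months is not a cap either: a three-month wait (13.0 weeks) would put the last class at about week 16. The documents do not show that such waits will occur. The study-procedures figure is missing from the text we have, so a stated limit cannot be ruled out.

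**Conclusion.** No change is needed. Counting follow-up from baseline is a fair choice for this pilot. It gives every randomised patient the same follow-up interval whether or not they attend, which suits the stated purpose of testing whether patients can be retained. Both arms wait, so a bias between them would need groups to fill at different speeds by arm, and nothing in the documents suggests that. The effect sizes are correct for what they are labelled as, 16 and 24 weeks from baseline. C.2.3 assigns the test of maintenance to the full-scale trial; if that trial keeps the same schedule, these are the planning figures it needs.

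What remains is a gap that an analyst would ordinarily fill by describing the waits and coding time by visit or by actual weeks. Following the plan as written yields no wrong result. The mixing of times since treatment is real: a spread of about 4.3 weeks with waits up to one month, or 8.7 with waits up to two. Its effect on the 16-week estimate is 0.02 to 0.17 SD against a half-width of 0.57 SD. These figures rest on the assumed maximum waits, uniform enrolment, a three-week span of classes, linear loss of effect and 24 completers per arm.
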